3.3 Research questions

What is the proportion of participants who progressed as planned or successfully complete the program at 3, 6, and 10 years after start of the programme? What is the societal business case of the programme and what opportunities for improvement can be identified to optimize its sustainability through a qualitative analysis of the impact on both participants and hospital departments? To what extent do competencies across different domains provide insight into when a participant may require additional support? To what extent do conscious or unconscious racial microaggressions occur in the workplace and what opportunities exist to address and mitigate the unconscious form?

4. Study design

4.1 Mono- or multicenter study.	Monocenter study 	Multicenter study 
--	--	--

4.2 Retrospective study or prospective study		Retrospective study 	Prospective study 
4.3 Cross-sectional or follow-up study		Cross-sectional study 	Follow-up study 
4.4 Quantitative or qualitative study		Quantitative study 	Qualitative study 
4.5 Pilot or explorative study?	Not applicable 	Pilot study 	Explorative study 

Explain why it is a pilot or explorative study.

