6.5 Statistical and/or qualitative analysis			
Please specify Statistical Analysis Plan (SAP): a. Description of study population: The study population consists of nursing newcomers who are already enrolled or will enrol in the fast-track integration trajectory at UMCG and participating partner hospitals. This includes both asylum seekers and migrants. Demographic and baseline characteristics include age,			

gender, language proficiency, participant status (asylum seeker or migrant), and socioeconomic and employment background. Participants who provide consent for research purposes will be included in the analysis.

b. Description of preparation of the data for analyses:

Collected data will be pseudonymized and direct identifiers removed. Data cleaning will involve checking for completeness, consistency, and plausibility. Variables will be coded according to pre-specified categories (e.g. employment history, language level). Missing data will be handled using appropriate methods such as multiple imputation or sensitivity analyses, depending on the extent and pattern of missingness. For qualitative data from surveys or interviews, responses will be anonymized and transcribed for coding and thematic analysis.

c. Specify all applicable statistical and/ or qualitative methods. This usually requires an extensive description of the planned analyses and covariates:

Primary outcome analysis: Descriptive statistics and inferential analyses (e.g. proportions, means, standard deviations) will be calculated for successful trajectory completion, BIG registration achievement. Associations with baseline characteristics will be explored using logistic regression or other appropriate multivariable models.

Secondary outcome analysis: Qualitative data from the Regioplan survey will be analyzed using thematic analysis to identify patterns, facilitators, and barriers in the trajectory. Quantitative secondary measures (e.g. language progress, employment outcomes) will be summarized using descriptive statistics and, where appropriate, tested with regression models to explore predictors of success.

Subgroup analyses will consider variables such as asylum seeker vs. migrant status, age groups, gender, and baseline language proficiency.

d. Clarify how this analysis plan, study setup, sample size and design will answer the study questions:

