This analysis plan ensures that both primary and secondary outcomes are systematically evaluated. The prospective cohort design, together with a projected sample size of approximately 300 participants nationwide (80 in the Northern region), allows for sufficient statistical power to explore patterns of trajectory completion and integration success.

Qualitative analyses complement the quantitative results by providing in-depth understanding of barriers, facilitators, and contextual factors affecting trajectory outcomes. Together, these analyses will answer the research questions regarding the effectiveness, scalability, and potential optimization of the integration trajectory for nursing newcomers.

Has the statistical analysis section (6.5) been completed?

Yes

No

7. Recruitment and informed consent/objection

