 45. Where I work or go to school, I see few people of my racial background
 46. I notice that there are few people of my racial background on the TV, books, and magazines
 47. Sometimes I feel as if people look past me or don't see me as a real person because of my race
 49. I feel invisible because of my race
 51. I am ignored in school or work environments because of my race
 52. My contributions are dismissed or devalued because of my racial background
- The modified RMAS will be used.

Appendix 7: In the context of the qualitative analysis conducted by Regioplan, 17 participants were invited by the UMCG project coordinator to contribute. These participants completed a survey that was jointly developed by Regioplan and UMCG and were asked to participate anonymously. The following consent was requested: ' Beste deelnemer van het UMCG traject 'Nieuwkomers in hun kracht', Onderzoeksbureau Regioplan is bezig met een evaluatieonderzoek over het traject dat je aan het volgen bent. Hierin willen we meer leren over wat er goed gaat in het traject, en hoe we het traject nog beter kunnen

maken. Om hierachter te komen is jouw mening belangrijk. Daarom vragen wij je om deze vragenlijst in te vullen. Het invullen duurt ongeveer 20 minuten en je antwoorden worden helemaal anoniem opgeslagen. Je kunt dus alles zeggen wat je wil, zonder dat wij weten wie het antwoord heeft gegeven. Het kan zijn dat je deze vragenlijst al eerder hebt ingevuld. As dat zo is, vragen we je om hem weer in te vullen en hebben we een aantal aanvullende vragen voor je. Veel dank voor het meedoen aan het onderzoek!

Multiple choice questions used by Regioplan to survey the participants.

Questionnumber	
3	The program has – so far – met my expectations (1, Strongly disagree; 2, Disagree; 3, Neutral; 4, Agree; 5, Strongly agree; 6, Don't know)
5	How satisfied are you with how the intake at the language center went? (1, Very dissatisfied; 2, Dissatisfied; 3, Neither dissatisfied nor satisfied; 4, Satisfied; 5, Very satisfied; 6, I don't know)
6	How satisfied are you with the course of the interview to be able to participate in the program at the UMCG? (1, Very dissatisfied; 2, Dissatisfied; 3, Neither dissatisfied nor satisfied; 4, Satisfied; 5, Very satisfied; 6, I don't know)
8	How satisfied are you with the medical language program you have completed? (1, Very dissatisfied; 2, Dissatisfied; 3, Neither dissatisfied nor satisfied; 4, Satisfied; 5, Very satisfied; 6, I don't know)

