40	How satisfied are you with the training in general? (1, Very dissatisfied; 2, Dissatisfied; 3, Neither dissatisfied nor satisfied; 4, Satisfied; 5, Very satisfied; 6, I don't know) 4.7 (0.6)
43	To what extent can you apply the insights from the training in your work as a nursing assistant? (1, Not at all; 2, Not good; 3, Neither good nor bad; 4, Good; 5, Very good; 6, I don't know)
46	What do you think of the informal meetings that are occasionally organized to speak with other participants or stakeholders? (1, Very dissatisfied; 2, Dissatisfied; 3, Neither dissatisfied nor satisfied; 4, Satisfied; 5, Very satisfied; 6, I don't know)

Open questions used by Regioplan to survey the participants.

Questions
2. What does the program 'Newcomers in their Strength' mean to you?
4. In what ways does the program not meet your expectations?
7. Can you indicate what aspects of the intake and/or the interview to be able to participate in the program you are not or less satisfied with? And how would you improve this?
9. Can you indicate what aspects of the language program you are not/less satisfied with? Do you have a suggestion for improving this?
11. Can you indicate what support you are missing on the path to BIG registration?
16. Can you indicate what support you are missing in your work as a nursing assistant?
18. Can you explain your answer to question 17?
20. Can you explain your answer to question 19?
22. Can you explain your answer to question 21?
24. Can you explain why the program does not contribute to efficiently achieving your goal?
26. Can you explain in what way the tasks are not suitable for your level?
28. Can you explain why you would not recommend the program to other newcomers?
30. Can you explain why you would not start the program again or what makes you hesitant?
33. What could be improved about the orientation meeting?
35. What could be improved about the workplace skills training?
37. What could be improved about the peer review sessions?
41. Can you explain your answer to question 40?
42. What would you have liked to learn more about, or what would you like to learn more about, during the training?
44. Can you explain why you are unable to apply the insights effectively?
45. In what way can the re-entry training be improved?
47. Can you explain why you are not satisfied as answered in question 46?

48. In what way can these informal meetings be improved?

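### Most open questions in the participant survey ask only about shortcomings or improvements, so facilitators, which section 6.5 also promises, are under-elicited

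*Protocol*

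**What the plan says.** The aim is two-sided. Section 6.5c of the protocol plans a "thematic analysis to identify patterns, facilitators, and barriers in the trajectory" from the Regioplan survey. Section 6.5d says that the qualitative part will give "in-depth understanding of barriers, facilitators, and contextual factors affecting trajectory outcomes". The Dutch introduction to the participant survey in Appendix 7 tells respondents "Hierin willen we meer leren over wat er goed gaat in het traject": the evaluators want to learn what goes well. It adds that they also want to know how to make the programme better. The research question in section 3.3 is narrower and asks "what opportunities for improvement can be identified to optimize its sustainability through a qualitative analysis".

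The instrument is in Appendix 7. Participants receive rating items, nearly all on scales running from negative to positive, and 23 open questions. Some open questions are neutral, such as "Can you explain your answer to question 17". Most are not: "Can you explain why the program does not contribute to efficiently achieving your goal", "Can you explain why you would not recommend the program to other newcomers", "Can you indicate what support you are missing in your work as a nursing assistant". A separate buddy questionnaire follows in the same appendix.

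**The concern.** An open question largely sets what can be found in its answers. If a rating can be favourable or unfavourable but the follow-up asks only about the unfavourable side, the text for analysis holds reasons for dissatisfaction and few reasons for satisfaction. Themes will then lean towards barriers partly because of the wording.

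This matters for how the results are to be used. Section 3.1 wants the qualitative analysis and the business case to show where the benefits lie, as guidance for the period after philanthropic funding is phased out. That calls for knowing which elements to keep as well as which to repair. Appendix 2 describes pairing with nurse buddies and tailored support as parts of the programme, and these are among the elements for which participants get no specific prompt to say what helped.

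**Working it through.** The protocol gives no figure on this point, so the check is a count of the open questions in Appendix 7.

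**Participant survey.** The open questions are 2, 4, 7, 9, 11, 16, 18, 20, 22, 24, 26, 28, 30, 33, 35, 37, 41, 42, 44, 45, 47, 48 and 49, which makes 23.

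| Type | Questions | Number |
|---|---|---|
| Shortcoming only, after a two-sided rating | 4, 7, 9, 11, 16, 24, 26, 28, 30, 44, 47 | 11 |
| Improvement only | 33, 35, 37, 45, 48 | 5 |
| Arguable (what one would like to learn more about) | 42 | 1 |
| Neutral or two-sided | 2, 18, 20, 22, 41, 49 | 6 |

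- One-sided: 11 + 5 = 16, and 16/23 = 70%. With question 42: 17/23 = 74%.
- Neutral or two-sided: 6/23 = 26%.

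**Buddy survey.** Leaving out the numeric questions 3 and 4, there are 15 open questions. Seven are one-sided (6, 8, 10, 12, 13, 17, 26): 7/15 = 47%. Eight are neutral or two-sided (1, 2, 21, 28, 30, 32, 34, 35): 8/15 = 53%.

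**Both surveys.** The total is 23 + 15 = 38. One-sided: 16 + 7 = 23, and 23/38 = 61%. With question 42: 24/38 = 63%.

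**Where the gap falls.** Setting ratings beside their open follow-ups:

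| Rated element (items) | Open follow-up |
|---|---|
| Intake and interview (5, 6) | 7, shortcomings only |
| Language programme (8) | 9, shortcomings only |
| Support towards BIG registration (10) | 11, missing support only |
| Buddy, colleagues, head nurse (13 to 15) | 16, missing support only |
| Language learning at work, use of knowledge, getting to know the system (17, 19, 21) | 18, 20, 22, neutral |
| Re-entry training overall (40) | 41, neutral; 42 and 45 add wishes and improvements |

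For the first four rows, a participant who is satisfied can name what helped mainly through questions 2 and 49.

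**Skip logic.** Appendix 7 does not state the routing, but the tilt does not depend on it. If the one-sided follow-ups appear only after a poor rating, satisfied respondents get no prompt on that element. If everyone sees them, the wording presupposes a poor rating.

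**The case against.** The best defence is that the instrument suits its research question. Section 3.3 asks for opportunities for improvement, and questions on what to improve answer that directly. This stands for the five improvement questions. It does not cover the facilitators promised in sections 6.5c and 6.5d.

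A second defence is that positive material does have ways in. Questions 18, 20, 22 and 41 invite an explanation of any rating, question 49 asks outright about things going well, and question 18 follows an item on working with Dutch-speaking colleagues. Just over half of the buddies' open questions are neutral, and the ratings themselves record satisfaction. All of this is correct. A reader might infer from the wording that the survey is unable to show why satisfied participants succeed; the documents do not support that. Answers are stored anonymously, so tying them to individual trajectories would be limited under any wording.

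A reader might also take the figure 4.7 (0.6) beside item 40 as evidence that nearly everyone was satisfied and went unasked. It cannot carry that. The figure is unlabelled and has no number of respondents. Item 40 is followed by the neutral question 41. Answers of 4, 5 and 5 would already give a mean of 4.67 and an SD of 0.58, with nobody at 3 or lower.

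Finally, the survey was commissioned from an outside party, has already been used, and serves a secondary outcome that section 4.5 calls exploratory. This lowers the weight of the point but does not remove it.

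**Conclusion.** The point holds in a limited form. The protocol promises facilitators and barriers, while 70% to 74% of the participants' open questions, and 61% to 63% over both surveys, address only shortcomings or improvements. Facilitators are under-elicited, most clearly for intake, the language course, support towards BIG registration, and guidance on the ward. The range reflects one arguable question (42). The classification rests on the wording as printed in Appendix 7 and assumes no further prompts in the live questionnaire.

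Severity is minor. The primary outcome is untouched, and this is a cheap improvement to a secondary, exploratory aim.

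**What to change.** **Later rounds.** Section 7.2.2.2 speaks of a first analysis, section 8.4 of future ones, and the survey introduction allows for repeat completion. In those rounds, replace follow-ups 4, 7, 9, 11, 16, 24, 26, 28, 30, 44 and 47 with the neutral request to explain the rating, as already used in 18, 20, 22 and 41, and put it to all respondents. Let question 16 ask both which support helped and which was missing. The improvement questions can stay, since they serve section 3.3.

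**Data already collected.** Add a sentence to section 6.5 stating that the open participant questions mainly elicit barriers and improvements, so the balance of themes is not evidence on the balance of facilitators and barriers. Facilitator themes need not be confined to the six neutral questions; positive content volunteered elsewhere, and the buddies' answers, remain usable.

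**Cost.** Rewording existing questions, somewhat longer answers to code, and a change of wording between rounds that should be noted when rounds are compared.
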